Innovation: This study is innovative on several levels. It will be the first to evaluate psychometric properties of a parental version of the DSM-5 IGD criteria, a critical aspect of diagnosis for youth. In addition, this study will assess comorbidities of gaming, substance use, and related conditions, and it will evaluate changes in these symptoms and conditions over time. Most importantly, this study is novel in that it is the first randomized trial specifically for IGD. Based on the premises that parents can modify the child's environment to be less conducive toward game playing and more encouraging of non-gaming behaviors and that children are unlikely to seek treatment on their own, the study is directed toward parents. This study will provide unique and valuable information on the nature, course, and treatment of this putative new addictive disorder.

Approach

Subjects will be recruited by ads directed toward parents, e.g., "Worried about how much your child plays videogames?" Parents who call will be informed that the study specifically relates to an intervention directed toward parents, with child involvement encouraged but not required.

Inclusion criteria are: (1) parent/guardian of a 10-22 year old residing in the same household ≥ 8 months/year; and (2) reports the child plays videogames ≥ 15 hours/week on average and that the playing has caused significant problems in the family or with the child's school or work.

Exclusion criteria are: (1) parent or child has a significant other mental health condition that may impact response to this treatment (suicidality, psychotic disorder); (2) parent is unavailable to attend 6 weekly sessions over the next 8 weeks; or (3) parent is currently receiving (or has received in the past 3 months) psychosocial support related to parenting or family counseling.

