- Difficulties in Emotion Regulation Scale (DERS; Gratz & Roemer, 2004) a brief questionnaire about emotional regulation
- a modified Video Game Dependency Scale (VGDS; Rehbein et al., 2015) assesses parents' perceptions of their child's game playing
- a semi-structured clinical interview using DSM-5 criteria
- a calendar based assessment, the TimeLine Follow Back (TLFB; Sobell & Sobell, 1990) of the child's gaming and sleep patterns over the past 4 weeks
- Child Behavior Checklist (CBCL; Achenbach, 2001), an index of child competencies and emotional and behavioral difficulties that yields internalizing, externalizing, and total problem scores
- Conners' Parent Rating Scale—Revised (CPRS-R), a measure of emotional and behavioral problems, including ADHD
- parent version of the Behavior Rating Inventory of Executive Functioning (BRIEF; Guy et al., 2004) will evaluate executive function of their child
- Brief Family Assessment Measure (BFAM; Skinner et al., 1995, 2000) assesses perceptions of recent family functioning
- a brief autism spectrum screen (Allison et al., 2012)
- Quality of Life Inventory (Frisch et al., 1992) will assess their own quality of life
- caregiver's proxy report on the Questionnaire for Measuring Health-related Quality of Life in Adolescents (KINDL-R; Ravens-Sieberer, 2000) assesses perceived QoL of their child

Children who choose to participate will complete parallel instruments from their perspective:

- the VGDS (Rehbein et al., 2015) with additional specific items about gaming (Petry et al., 2014)
- a semi-structured clinical interview using DSM-5 criteria (Petry et al., 2014)
- a modified Teen Addiction Severity index (TASI; Kaminer et al., 1999)
- Perceived Social Support Scale (Procidano & Heller, 1983),
- BFAM (Skinner et al., 1995)
- Social Phobia and Anxiety Inventory for Children (Beidel et al., 1995),
- brief autism screen (Allison et al., 2012),
- Pittsburgh Sleep Quality Index (PSQI; Buysse, et al, 1989),
- Center for Epidemiological Studies-Depressed Mood scale (CES-D; Radloff, 1977; Thomas et al., 2001)
- Youth Self-Report (YSR; Achenbach, 1991) of emotional and behavioral problems
- Difficulties in Emotion Regulation Scale (DERS; Gratz & Roemer, 2004; Weinberg & Klonsky, 2009)
- a calendar based assessment, the TimeLine Follow Back (TLFB; Sobell & Sobell, 1990) of gaming and sleep patterns over the past 4 weeks

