Randomization. After completing the baseline evaluation, parents will be randomized to one of two interventions outlined below. Groups will be stratified based on age of child (<18 or over), and whether or not the child agreed to participate in the study at baseline.

A. Referral for care. Participants assigned to this condition will be referred to support groups in the local area for parents of children with addiction problems such as DMHAS, NAMI and Parents Opening Doors. Parents who express concerns about other mental health problems of their child will be referred for appropriate services as well, e.g., for depression, ADHD, autism, substance use, conduct disorder, etc. After four weeks, the research team will call parents in Group A to inquire about whether they have questions about the referral list or need additional information on treatment providers.

B. Behavioral therapy. This intervention will be administered in 6 individual and/or family sessions (depending on child's willingness to participate), the contents of which are outlined in Petry (under review). Session 1 will focus on reviewing information collected at baseline and orienting the parent (and child, when applicable) to treatment. Parents will be reminded that although they cannot prevent playing games entirely, they can learn to better understand why their child is playing. Through this process they may alter their own reactions toward playing, which in turn may decrease the extent to which their child plays and the problems arising from it. Therapists will review a tracking form with parent and instruct them how to monitor their child's game playing over the upcoming week. Children who participate in the first session will be asked to keep their own independent log of their game playing behaviors as well.

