Data Analyses. We will evaluate potential baseline differences between groups despite random assignment, and any that exist that may relate to outcome will be used as covariates or fixed factors. Analysis will be conducted on an intent-to-treat basis, using all randomly assigned subjects. Both during treatment (baseline to post-treatment) and longer-term (month 4) efficacy will be evaluated.

Aim 1: To evaluate the feasibility and acceptability of this intervention, the proportion of parents assigned to the intervention who complete 6 sessions will be examined, as will the proportion of youth who attend the sessions. Parent and child ratings of satisfaction with the intervention will be assessed.

Aim 2: To examine the effect size of the intervention on reducing gaming, parental reports of proportion of days on which their child played games and durations of game playing will be compared between conditions, controlling for baseline indices. These are continuous measures, with missing data likely. Hierarchical linear models (HLM; Gibbons et al., 1993) will analyze differences between groups over time. These analyses have advantages over repeated measures as they estimate missing data via model parameter estimates and use real time, as opposed to scheduled time, of assessments. Analyses will be conducted for both short and long-term effects. The model will include factors representing group (using contrasts above), time, and the interaction of group by time, along with any important covariates.

Exploratory aims are to assess the effect size of the intervention on secondary outcomes including CBCL scores, family communication, psychosocial functioning and quality of life. Using similar HLM analyses as outlined above we will compare groups over time on these indices.

Power analyses. This pilot study is designed to assess feasibility and effect sizes. Twenty subjects per group are sufficient to assess effect sizes, and if medium or larger effect sizes are noted, subsequent larger scale psychotherapy development trials will be proposed to evaluate short and long-term efficacy of this intervention.

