Data quality control/exploratory analyses: Instruments chosen for this study are reliable and valid for assessing psychosocial problems and gaming behavior, although the parental version of the VGDS is new. Careful training of evaluators will precede study initiation, and assessment interviews will be audiotaped and rated for reliability when participants agree to taping.

Valid assessment requires that measures are obtained from different sources. Parent and child reports will be compared using Kappa's for diagnostic assessments, and Shrout and Fleiss intraclass correlations for continuous variables. We expect most children will participate, with ≥ 30 parent-child pair reports anticipated. In addition to comparing patient and child reports, responses to semi-structured clinical interviews will be compared with VGDS responses.

Future directions. This study will inform development of interventions for Internet gaming disorder. Very little systematic research has been conducted on this condition, and this study will be the first of its kind. It will lead to a therapy manual and specify procedures for monitoring therapy delivery and evaluating potential mechanisms of change for parents of children with the condition. Using established methods of psychotherapy development (Rounsaville et al., 2000), we will determine the initial feasibility and effect size of this behavioral intervention. This work will also guide further development of assessment instruments for IGD. This study holds potential to pave the way for future research evaluating the biological underpinnings of IGD and its association with substance use disorders, as well as its treatment.

References

Achenbach, T. M. (1991). *Manual for the youth self-report and 1991 profile* Department of Psychiatry, Burlington, VT: University of Vermont.

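### Several exploratory scales are titled for children, teens or adolescents, yet families of 18–22 year olds are pooled in with no adult form, no scoring rule and no age-stratum term in the model

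*Combined protocol and SAP*

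**What the plan says.** - **Who is enrolled.** The inclusion criteria under Approach admit a "parent/guardian of a 10-22 year old residing in the same household ≥ 8 months/year". The next paragraph defends the width of the range on the ground that resident young adults probably still depend on their parents for money, which makes the intervention relevant to them. It does not discuss measurement.
- **How they are randomised.** Under Randomization: "Groups will be stratified based on age of child (<18 or over". Whether the child takes part is the second stratification factor.
- **What is measured.** The Assessments section lists one battery for all ages. The parent completes the "Child Behavior Checklist (CBCL; Achenbach, 2001), an index of child competencies and emotional and behavioral difficulties that yields internalizing, externalizing, and total problem scores", and also a proxy KINDL-R, the "Questionnaire for Measuring Health-related Quality of Life in Adolescents". The participating child completes the Youth Self-Report (YSR), a modified Teen Addiction Severity Index (TASI) and the "Social Phobia and Anxiety Inventory for Children" (SPAI-C below). No alternative version for offspring aged 18 or over is named.
- **How it is analysed.** Data Analyses specifies intention to treat on all those randomised. Hierarchical linear models (HLM) are applied to "secondary outcomes including CBCL scores, family communication, psychosocial functioning and quality of life". The model terms are group, time, their interaction and any important covariates. The only stated trigger for a covariate is a baseline group difference that may relate to outcome.
- **What is claimed for the instruments.** Data quality control states: "Instruments chosen for this study are reliable and valid for assessing psychosocial problems and gaming behavior". The one qualification is that the parental version of the gaming scale is new. No age limit is given.

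**The concern.** Adult offspring are in the trial by design, and the protocol thinks age 18 important enough to stratify on it. Yet the plan does not say which form or which score (raw or age-normed) applies to them, or how the two age strata are combined.

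This leaves a choice to be made after the data are in: keep, convert or drop the adult scores. In a trial of 40 families, each option can move an effect size. Specific aims says that a medium or larger effect on gaming or on psychosocial functioning may lead to a larger study, so some of these exploratory estimates can feed a stated decision. CBCL is the only instrument that Data Analyses names among the exploratory outcomes, and KINDL-R is the only listed scale for the child's own quality of life as the parent sees it.

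**Working it through.** **Plan's own figure.** Power analyses states 20 subjects per group. It gives no alpha, power, SD, precision target or dropout rate, so the figure cannot be reproduced. It is used below only as the starting n.

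**Inputs from the documents.** 20 per group; ages 10–22; stratum boundary at 18; a medium effect as the mark for going forward.

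**Assumptions (not in the documents).** Medium means d = 0.50. Intervals are at 95%. The share f of families with offspring aged 18–22 is shown from 10% to 50%. An even spread of ages over 10–22 would give 5/13 = 38%, but the residence rule excludes college students living away, which plausibly makes the share smaller.

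**Case 1: adult scores missing or unusable.** n per arm = 20(1 − f); half-width = 1.96 × √(2/n + d²/(4n)).

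| f | n per arm | Half-width at d = 0.50 | Relative to 20 per arm |
|---|---|---|---|
| 0 | 20 | 1.96 × √(0.1000 + 0.0031) = 0.63 | 1.00 |
| 10% | 18 | 1.96 × √(0.1111 + 0.0035) = 0.66 | 1.05 |
| 20% | 16 | 1.96 × √(0.1250 + 0.0039) = 0.70 | 1.12 |
| 30% | 14 | 1.96 × √(0.1429 + 0.0045) = 0.75 | 1.20 |

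The ratio is 1/√(1 − f), whatever the starting n. It therefore applies equally to the child-completed forms, where fewer than 40 reports are expected (the protocol anticipates at least 30 parent–child pairs). At the even-spread share of 38% it would be √(13/8) = 1.27.

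**Case 2: adult scores kept but less reliable.** If the form shows d = 0.50 under 18 and has relative reliability r in adults, the pooled value is about 0.50 × [(1 − f) + f√r].

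| f | r = 0.7 (√r = 0.837) | r = 0 |
|---|---|---|
| 10% | 0.50 × (0.90 + 0.084) = 0.49 | 0.45 |
| 20% | 0.50 × (0.80 + 0.167) = 0.48 | 0.40 |
| 30% | 0.50 × (0.70 + 0.251) = 0.48 | 0.35 |
| 50% | 0.50 × (0.50 + 0.418) = 0.46 | 0.25 |

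The last column assumes that the form registers no treatment effect at all in an 18–22 year old. It is a bound, not an expectation.

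**Yardstick.** With all 20 per arm, the interval around 0.50 already runs from 0.50 − 0.63 = −0.13 to 0.50 + 0.63 = 1.13. A shift of 0.01 to 0.04 is small beside that.

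**Does the planned model bring in age?** Covariates enter when the groups differ at baseline. Stratifying on age makes a group difference in age unlikely, so the stated rule will probably leave the stratum out.

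**The case against.** The case on the other side is substantial, and most of it limits the point rather than removing it.

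- **No age limits are given.** A reader might infer that the adult stratum has no age-appropriate score. The documents do not support this: no upper age is stated for any form, the TASI is described as modified in ways not shown, and the protocol itself uses the word child for offspring up to 22. What stands is that the titles point to younger respondents and that the plan is silent on ages 18–22.
- **Many exploratory measures are not affected.** The BFAM, the parent's own Quality of Life Inventory, and the child's CES-D, PSQI, DERS and social support scale are not child forms by title. Psychosocial functioning is not tied to any one form. This stands, and it confines the point to the five forms named.
- **The comparison between arms is protected.** Stratification tends to balance adults across arms, a comparison of change does not need age norms, and scores missing by a baseline stratum narrow the population without favouring an arm. This stands. The remaining issues are precision, interpretation and an unplanned choice, not bias between arms.
- **Important covariates are already allowed.** This does not settle the matter, because the only stated trigger is a baseline difference that stratification makes unlikely.
- **Restricting the analysis to under-18s would be worse.** Making them the main set would drop randomised families by rule and depart from the stated intention-to-treat analysis. This stands, and the fix below does not do so.

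**Conclusion.** The gap is real but limited. For CBCL, YSR, TASI, SPAI-C and KINDL-R, the plan enrols and stratifies 18–22 year olds, lists no adult form or scoring rule, and does not commit to the age stratum in the model.

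The consequence for these exploratory effect sizes may be small (0.50 seen as 0.46–0.49 at reliability 0.7 in adults, for shares of 50% down to 10%) or moderate (intervals about 5–20% wider if scores are missing for 10–30% of families). Both ranges rest on assumed adult shares, and the first also on an assumed reliability.

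A reader might go further and conclude that these effect sizes are in fact diluted, or that adult families are in fact lost. The documents give neither the adult share nor the handling of their scores, so neither can be asserted. The Aim 2 outcomes, parent-reported gaming days and durations, are not taken on these forms and are unaffected, as is the gaming part of the go-forward criterion.

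**What to change.** In Data Analyses, for the five forms:

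1. Keep all randomised families as the main analysis set.
2. Include the randomisation age stratum (under 18 versus 18 or over) as a factor in the HLM, whether or not a baseline difference is seen.
3. Use raw rather than age-normed scores when pooling over strata.
4. Report the estimate and the contributing n by stratum, with an under-18-only estimate as a sensitivity analysis.

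In Data quality control, limit the reliability and validity statement to the ages that each form covers.

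**Cost.** A few sentences and one more model term, with no new visits or instruments. The stratum-level results will be imprecise and should be labelled descriptive. At an assumed adult share of 30% there would be 6 per arm aged 18 or over, with a half-width of about 1.96 × √(2/6 + 0.25/24) = 1.15. The under-18 sensitivity estimate would carry the wider intervals of Case 1.

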2. To examine the effect size of the intervention for reducing gaming. Parental reports of their child's frequencies and durations of game playing behaviors will be compared over time between conditions to establish effect size estimates.

Exploratory aims are to assess the effect size of the intervention on secondary outcomes, including indices of

substance use, conduct and attention problems, family communication, psychosocial functioning and quality of life. In addition, we will evaluate concordance between parental and child reports on measures of gaming and gaming problems. These data will help inform development of parent assessment tools for IGD.

Results from this pilot trial will be used to guide future grant applications. If data are promising, we will improve and modify the intervention based on parent and child feedback. If medium or larger effect sizes are detected for decreasing gaming or improving psychosocial functioning, a larger scale, longer-term study may be proposed. Even in the absence of treatment-specific effects, these results will provide valuable information about how gaming and psychosocial problems change over time. Given increasing scientific interest in this condition, this study is timely and critical for addressing concerns related to this emerging public health issue.

Background and significance

The vast majority of children, along with many young adults, play video or electronic games. A nationally representative study of US youth between the ages of 8 and 18 found that 88% played games electronically, and 68% played at least weekly and 23% daily (Gentile, 2009). Although most videogame playing is harmless, excessive play can lead to psychosocial and even medical problems, with reports of game-induced seizures and even deaths (Chuang, 2006; BBC News; Reuters). Although very few cases rise to these extremes, governments of some Asian countries have declared excessive game playing to reach near epidemic proportions, and treatment clinics have been established around the world, including the US.

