Although understanding of IGD is in its early stages, male gender is clearly a risk factor. No matter how IGD is defined all studies find higher rates in males than females (Desai et al., 2010; Choo et al., 2010; Mentzoni et al., 2011). In the DSM-5 based evaluation of IGD in German adolescents (Rehbein et al., 2015), 2.0% of males were classified with the condition versus 0.3% of females. Younger age is consistently associated with gaming as well. Using less stringent classification systems, Festl et al. (2011) found that youth under 19 years had a 7.6% prevalence rate of gaming problems, and for those 20 years and older rates were 3.7%. Mentzoni et al. (2011) noted that 15.4% of males aged 16-21 years, and 9.7% of males aged 22-27, had gaming problems, while rates in all other age and gender groups were under 3%.

Depression and social isolation appear related to IGD. In cross sectional studies, persons with gaming problems have higher rates of depression than those without (Desai et al., 2010; Mentzoni et al., 2011; van Rooij et al., 2010). Low sociability and social competence also correlate with gaming problems (Festl et al., 2011; Lemmens et al., 2009; Rehbein et al., 2010). Lo et al. (2005) surveyed 174 Taiwanese college-age online game players and found that quality of interpersonal relationships decreased, and social anxiety

intensified, as game playing increased. Romer et al. (2013) found that heavy game playing was associated with an increase in depression over time, and that greater depression also predicted more game playing as well as withdrawal from sports and other organized activities in over 700 US youth.

Gaming problems are also linked to impulsivity and Attention Deficit Hyperactivity Disorder (ADHD; Choo et al., 2010; Gentile, 2009; Rehbein et al., 2010). In a prospective study, Swing et al. (2010) evaluated gaming and attention problems in over 1,300 children aged 6 to 12 years old. Game playing correlated with more attention problems at the initial interview, and this relationship persisted throughout a 13-month period.

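### The two randomisation strata are not named in the Aim 2 model, and the remaining covariates are left open until baseline group differences have been seen

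*Combined protocol and SAP*

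**What the plan says.** In the combined protocol and SAP:

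- **Randomization:** "Groups will be stratified based on age of child (<18 or over), and whether or not the child agreed to participate" at baseline. Two binary factors give four strata.
- **Data Analyses, opening paragraph:** baseline differences between the arms are examined, and "any that exist that may relate to outcome will be used as covariates or fixed factors".
- **Data Analyses, Aim 2:** the gaming outcomes "will be compared between conditions, controlling for baseline indices". On the hierarchical linear model: "The model will include factors representing group (using contrasts above), time, and the interaction of group by time, along with any important covariates".
- **Exploratory aims:** the secondary outcomes use a similar model, so they inherit the same covariate rule.
- **Power analyses:** "if medium or larger effect sizes are noted, subsequent larger scale psychotherapy development trials will be proposed". Specific aims says likewise that, on such a result, "a larger scale, longer-term study may be proposed".

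The baseline value of the outcome is therefore the only covariate fixed in advance. No analysis text names child age stratum or child participation. There is no candidate list, imbalance test, threshold or criterion for relevance to outcome.

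**The concern.** There are two separate problems.

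**The strata.** Stratified allocation removes the strata's contribution from the sampling variance of the group difference. A model that omits them leaves that contribution in the residual variance. If the strata are prognostic beyond baseline, the point estimate hardly moves, but its standard error is overstated, the interval is too wide and the test is conservative. The covariate rule cannot repair this, because it is triggered by imbalance and these factors are balanced by design.

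The documents make some prognostic value plausible. Risk factors says "Younger age is consistently associated with gaming as well". For the intervention arm, "This intervention will be administered in 6 individual and/or family sessions", depending on whether the child is willing. They give no size.

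**The open rule.** Beyond the baseline value, the covariate set is decided after the arms have been compared at baseline, on unstated criteria. Two analysts could follow the text faithfully and report different effect sizes from the same data. Aim 2 exists to produce that effect size, and its magnitude decides whether a larger trial is proposed.

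**Working it through.** The plan states no figure on this point to reproduce, so the check compares the text (above) and sizes the consequence by simulation.

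**Inputs from the documents:** 40 families, 20 per arm (Power analyses); two stratifying factors (Randomization); about 75% of children participating, from at least 30 parent-child pairs among 40 (Data quality control/exploratory analyses); baseline adjustment (Aim 2).

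**Assumptions:** 25% of children aged 18 or over; permuted blocks of 4 within strata; correlation 0.5 between any two visits; outcome SD 1; complete data unless stated. R² is the share of outcome variance left after baseline that the strata explain.

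**1. Expected size.** In a week-8 ANCOVA the residual variance is 1 − 0.5² = 0.75.

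- Without strata, SE ≈ √(0.75 × 2/20) = 0.274.
- With strata at R²=0.20, SE ≈ √(0.75 × 0.80 × 2/20) = 0.245.

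Simulated mean SEs are 0.277 and 0.248. The half-widths are 2.026 × 0.277 = 0.56 (37 df) and 2.030 × 0.248 = 0.50 (35 df).

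**2. Simulated ANCOVA, 12,000 trials per setting, without → with strata**

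| R² | CI half-width (SD) | Null rejection | Power at d=0.5 |
|---|---|---|---|
| 0 | 0.56 → 0.56 | 5.4 → 5.4% | 42.0 → 41.5% |
| 0.05 | 0.56 → 0.55 | 4.5 → 5.1% | 40.7 → 42.2% |
| 0.10 | 0.56 → 0.53 | 3.7 → 4.8% | 42.1 → 45.6% |
| 0.20 | 0.56 → 0.50 | 3.3 → 5.0% | 40.7 → 49.3% |

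Monte Carlo error on power is about √(0.42 × 0.58/12,000) = 0.45 points. At R²=0.20 without strata, the mean reported SE is 0.277 but the estimate's actual SD is 0.253, so the SE is overstated by 0.277/0.253 − 1 = 9%. With strata the two agree (0.248 and 0.251). RMSE is almost unchanged (0.253 and 0.250): what is lost is mainly honest reporting of precision.

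**3. Longitudinal readings.** The text allows two.

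- *(i) Week 8 and month 4 as outcomes, baseline as covariate, strata as main effects.* SE falls from 0.276 to 0.262 at R²=0.10 and to 0.247 at 0.20. Power rises from 42.9 to 47.0% and from 42.0 to 51.1%.
- *(ii) Baseline as one of three outcomes, with strata-by-time terms.* SE falls from 0.316 to 0.309 and to 0.301. Power rises from 34.5 to 36.1% and from 33.2 to 37.1%, about half the gain. Strata main effects alone do not change the precision here, because the group-by-time contrast is a within-family change and constant terms cancel.

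**4. Would the plan's rule admit the strata?** An imbalance test at p<0.10 picks up either factor in 0-1.4% of trials, most often when one level holds only 10% of children.

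**5. Sensitivity.** The ANCOVA was varied over block sizes 2, 6 and 8, an 18-or-over share of 10% or 40%, participation of 90%, and 20% missing data. The power gain is 3.0-4.0 points at R²=0.10 and 7.4-9.1 at 0.20. The loss at R²=0 is 0.3-1.3 points.

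**6. The covariate rule.** The parent list under Assessments has 15 entries. With 15 independent variables screened at an assumed 0.05, the chance of at least one apparent difference is 1 − 0.95¹⁵ = 54%.

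The rule was simulated in 6,000 trials with 15 independent scales, 3 of them prognostic (coefficient 0.25), and d=0.5. Four readings were compared: imbalance at p<0.05 or p<0.10, with relevance either known or judged from the trial's own outcomes at p<0.10.

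- The four disagree in 32.7% of trials, with a mean range of 0.153 SD when they do. With coefficient 0.15 the figures are 34.8% and 0.129 SD.
- Where a covariate enters and relevance is known, RMSE falls from 0.299 to 0.270 (p<0.05) and from 0.293 to 0.264 (p<0.10). With coefficient 0.15 it stays about level.
- The mean estimate is 0.500 when relevance is known. It is 0.486 (p<0.05) or 0.476 (p<0.10) when relevance is judged from outcomes.

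**The case against.** **Omitting the strata does not reach the decision.** The trigger for a larger study reads as a point estimate, which omission barely changes. The plan states no alpha and no confirmatory test, so power and null rejection describe a test it does not specify. This stands and limits the stakes. An effect size still needs an interval, and that interval would be misstated if the strata are prognostic.

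**The evidence that they are prognostic is thin.** The age link comes from surveys with age bands that do not split at 18, whereas this trial enrols only heavy players and already adjusts for baseline gaming. Individual versus family sessions exist only in the intervention arm, which points partly to effect modification rather than a common main effect. This also stands, and it is why the result is given over a range of R² that includes zero.

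**The factors are not excluded.** The model sentence's open allowance for important covariates would permit them. That is true, but permission is not commitment, and the only stated selection rule works against them.

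**The rule is milder than 30-35% suggests.** Averaged over all trials, the range between readings is about 0.05 SD (0.327 × 0.153), against an SE near 0.28. The readings fall on opposite sides of 0.5 in about 7% of trials. Changing only the threshold alters 13-15% of estimates, and two of the four readings assume perfect knowledge of relevance. These points are fair. Against them, disagreement rises to 37-46% if the scales are correlated at 0.4. The rule as written refers to baseline differences, not outcome differences; selection on outcomes is left possible, not prescribed.

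**Conclusion.** The concern holds in both parts, as a matter the sponsor should correct rather than a threat to the trial's validity.

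The plan stratifies on two factors, does not commit to adjusting for them, and relies on a covariate rule that will almost never bring them in. The loss depends on an R² that the documents do not give: negligible at 0.05 or below, about 3-4 points of power at 0.10, and about 7-9 points at 0.20 with a half-width of 0.56 instead of 0.50. If baseline is modelled as an outcome, the gain from adjusting is about half as large. Omission introduces no material bias, and its error is on the conservative side.

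The open covariate rule is a defect whatever R² is. It does not worsen the estimate on average, but it lets the reported effect size depend on unstated choices, and it adds a small downward bias if relevance is judged from the trial's own outcomes. Confidence in the sizes is moderate, since block size, age mix, visit correlation and the prognostic strength of the scales are all assumed.

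**What to change.** Replace the covariate rule in Data Analyses with wording to this effect:

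> All outcome models adjust for the baseline value of the outcome, child age stratum (under 18; 18 or over) and child participation at baseline (yes; no). If baseline is modelled as one of the repeated outcomes, each stratum factor also enters by time. Any further covariates form a short list chosen on prior prognostic grounds and fixed before outcomes are compared by group. Adjustment prompted only by an observed baseline difference is a labelled sensitivity analysis, using a stated imbalance criterion.

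The cost is SAP wording. Both factors are already recorded for randomisation. Adjustment uses two degrees of freedom, or six parameters with time interactions over three visits. If the strata turn out not to be prognostic, power is 41.5% instead of 42.0% with complete data, and 32.7% instead of 34.0% with 20% missing.

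The optional list must be short. Against 41.6% power with baseline and strata only, three listed covariates (coefficient 0.25 where prognostic) give 48.8% if all three are prognostic, 41.2% if one is and 38.2% if none is.
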